6.6. Lost to Follow-up

The Investigator must make every effort to contact patients who fail to return for scheduled visits so that they will not be declared "lost to follow-up." Patients will be considered "lost to follow-up" only after reasonable, documented attempts to reach the patient prove unsuccessful. These attempts include, but are not limited to, the following:

1. Contact all telephone numbers for the patient and their listed contacts (to be collected in the source at the patient's entry into the study), as applicable.

2. Contact the patient's primary care physician, referring specialist, or other healthcare professional, as applicable.
3. Send email, text, and postal mail with certified letters to all the patient's addresses and contacts, as applicable.
4. Review available medical records/notes for details of hospitalizations, clinic visits, or other procedures that may indicate the status of the patient, as applicable.
5. Utilize the internet to search for additional contact information, as applicable.
6. Check local, regional, and national public records to locate the patient or search for mortality status as allowed by law, as applicable.

The information and dates of attempted contact must be recorded in the patient's records and the patient's final status recorded in the appropriate eCRF. Once these actions have been exhausted and documented, the Sponsor or Sponsor's designee should be contacted for additional guidance.

7. PATIENT POPULATION AND SELECTION

Eligibility must be confirmed, and signed/dated informed consent obtained, prior to any study-related procedure. Where applicable, this includes the patient beginning the 2-week washout from RAAS inhibitors.

For patients who require RAAS inhibitor washout, certain evaluations at Visit 3 (randomization) may no longer fall within the limits set by the inclusion/exclusion criteria. These patients will remain eligible for the study based on their screening results, unless at Visit 3 they have a positive pregnancy test (positive urine pregnancy tests will be confirmed by a serum test) or have experienced the occurrence of any medical condition or circumstance that, in the opinion of the Investigator, exposes them to substantial risk and/or does not allow them to adhere to the requirements of the protocol.

If in the Investigator's opinion, a laboratory value at screening is deemed unlikely to be representative of the patient's true status, the Investigator may repeat the measurement on that variable through the central laboratory to assess patient eligibility. The Investigator is required to consult with the Medical Monitor for more than 1 repeat measurement to be permitted. In particular, RAAS inhibitors affect protein excretion and eGFR. If, in the Investigator's opinion, withdrawal of RAAS inhibitor may alter these variables sufficiently to meet eligibility criteria, the patient may, if willing, undergo RAAS inhibitor washout and be retested for UP/C and/or eGFR to assess eligibility prior to potential randomization.

7.1. Criteria for the Study

7.1.1. Inclusion Criteria

A patient will meet all of the following criteria to be eligible for this study.

1. The patient or parent/legal guardian (as appropriate) is willing and able to provide signed informed consent, and where required, the patient is willing to provide assent, prior to any screening procedures.
2. The patient has biopsy-proven FSGS lesion(s) or documentation of a genetic mutation in a podocyte protein associated with FSGS. The biopsy may have been performed at any time in the past. The patient will be enrolled based on light microscopy diagnosis of FSGS and supportive findings on either electron microscopy (EM) or immunofluorescence (IF) analysis (preferably both). In exceptional cases, the patient may be enrolled based on light microscopy diagnosis of FSGS lesion(s) in the absence of EM or IF analysis, provided the history and/or the course of the disease are indicative of primary FSGS and the case has been reviewed by the Medical Monitor and Investigator.
3. Sites within the US and UK: The patient is male or female aged 8 to 75 years, inclusive, weighing ≥ 20 kg, at screening.
Sites outside the US and UK: The patient is male or female aged 18 to 75 years, inclusive, weighing ≥ 20 kg, at screening.
4. The patient has a UP/C ≥ 1.5 g/g (170 mg/mmol) at screening.
5. The patient has an eGFR ≥ 30 mL/min/1.73 m² at screening.

6. The patient has a mean seated blood pressure $\geq 100/60$ mmHg and $\leq 160/100$ mmHg (patients ≥ 18 years of age) or between the 5th and 95th percentile for age, sex, and height (patients < 18 years of age; [Banker 2016](#)).
7. Women of childbearing potential (WOCBP), beginning at menarche, must agree to the use of 1 highly reliable (ie, can achieve a failure rate of $< 1\%$ per year) method of contraception from 7 days prior to the first dose of study medication until 90 days after the last dose of study medication. Examples of highly reliable contraception methods include stable oral, implanted, transdermal, or injected contraceptive hormones associated with inhibition of ovulation, or an intrauterine device (IUD) in place for at least 3 months. One additional barrier method must also be used during sexual activity, such as a diaphragm or diaphragm with spermicide (preferred), or male partner's use of male condom or male condom with spermicide (preferred), from Day 1/Randomization until 90 days after the last dose of study medication. WOCBP are defined as those who are fertile, following menarche and until becoming postmenopausal unless permanently sterile; permanent sterilization methods include hysterectomy, bilateral salpingectomy, and bilateral oophorectomy. A postmenopausal state is defined as amenorrhea for more than 24 consecutive months without an alternative medical cause; women on hormone replacement therapy must have a documented plasma follicle-stimulating hormone level > 40 mIU/mL. All WOCBP must have a negative serum pregnancy test at Screening (Visit 1), and a negative urine pregnancy test, with positive results confirmed by serum, at every study visit from Randomization (Visit 3) and after.
NOTE: Prior to menarche, pregnancy testing and contraceptive use are not required. However, the patient and their parent/guardian must be advised that, immediately upon menarche, the patient will be required to begin pregnancy testing and initiate contraceptive use. This requirement cannot be avoided.

7.1.2. Exclusion Criteria

A patient who meets any of the following criteria will be excluded from this study.

1. The patient has FSGS secondary to another condition.
2. The patient is ≥ 18 years of age and has positive findings on serological tests that, in the Investigator's opinion, are diagnostic of another primary or secondary glomerular disease. These may include: antinuclear antibody, anti-double stranded deoxyribonucleic acid (DNA) antibodies, complement C3 and C4, anti-neutrophil cytoplasmic antibody, rheumatoid factor, anti-glomerular basement membrane antibodies, any clinically significant abnormalities identified by serum and urine protein electrophoresis or immunofixation, or serum kappa and lambda free light chains. At the Investigator's discretion, these tests may be performed in patients < 18 years of age under clinically relevant circumstances.
3. The patient has a history of type 1 diabetes mellitus, uncontrolled type 2 diabetes mellitus (hemoglobin A1c [HbA1c] $> 8\%$), or non-fasting blood glucose > 180 mg/dL (10.0 mmol/L) at screening.
4. The patient has undergone any organ transplantation, with the exception of corneal transplants.

5. The patient requires any of the prohibited concomitant medications (see [Section 15.2.1](#)).
6. The patient has been treated with rituximab, cyclophosphamide, or abatacept within ≤ 3 months prior to screening. If a patient is taking other chronic immunosuppressive medications, the dosage must be stable for ≥ 1 month prior to screening and during the screening period.
7. The patient has a documented history of heart failure (New York Heart Association Class II-IV) and/or previous hospitalization for heart failure or unexplained dyspnea, orthopnea, paroxysmal nocturnal dyspnea, ascites, and/or peripheral edema.
8. The patient has clinically significant cerebrovascular disease (transient ischemic attack or stroke) and/or coronary artery disease (hospitalization for myocardial infarction or unstable angina, new onset of angina with positive functional tests, coronary angiogram revealing stenosis, or a coronary revascularization procedure) within 6 months prior to screening.
9. The patient has hemodynamically significant valvular disease.
10. The patient has jaundice, hepatitis, or known hepatobiliary disease (excluding asymptomatic cholelithiasis), or alanine aminotransferase (ALT) and/or aspartate aminotransferase (AST) > 2 times the upper limit of the normal range at screening.
11. The patient is positive at screening for the human immunodeficiency virus (HIV) or markers indicating acute or chronic hepatitis B virus (HBV) infection (acute HBV is defined as a positive hepatitis B surface antigen [HBsAg], hepatitis B “e” antigen [HBeAg], HBV DNA in blood or liver, or immunoglobulin M hepatitis B core antibody; chronic HBV is defined as a positive HBsAg and/or HBeAg and/or HBV DNA) or hepatitis C virus (HCV) infection (defined as reactive anti-HCV antibody and HCV RNA).
12. The patient has a history of malignancy other than adequately treated basal cell or squamous cell skin cancer or cervical carcinoma within the past 2 years.
13. The patient has a screening hematocrit value $< 27\%$ (0.27 L/L) or hemoglobin value < 9 g/dL (90 g/L).
14. The patient has a screening potassium value of > 5.5 mEq/L (5.5 mmol/L).
15. The patient is extremely obese (ie, ≥ 18 years of age with a body mass index [BMI] > 40 kg/m², or < 18 years of age with a BMI in the 99th percentile plus 5 units at screening), in whom, in the Investigator’s opinion, there is a causal relationship between obesity and development of the FSGS lesion. For patients with moderate or severe edema, BMI will be calculated based on remission or premonitory weight measured within 3 months prior to screening, if available. If not available, BMI will be calculated based on the estimated dry weight, based on the Investigator’s clinical judgment.
16. The patient has a history of alcohol or illicit drug use disorder (as defined in the Diagnostic and Statistical Manual of Mental Disorders, 5th Edition), or a reported habitual alcohol intake greater than 21 units/week within 2 years prior to screening.

17. The patient has a history of serious side effect or allergic response to any AngII antagonist or ERA, including sparsentan or irbesartan, or has a hypersensitivity to any of the excipients in the study medications.
18. The female patient is pregnant, plans to become pregnant during the course of the study, or is breastfeeding.
19. The patient has participated in a study of another investigational product within 28 days prior to screening or plans to participate in such a study during the course of this study.
20. The patient has had prior exposure to sparsentan.
21. The patient, in the opinion of the Investigator, is unable to adhere to the requirements of the study, including the ability to swallow the study medication capsules whole.

Patients with a medical condition or abnormal clinically significant laboratory screening value not listed above that may interfere with the evaluation of sparsentan efficacy or safety will be reviewed with the Medical Monitor before consideration of the patient for enrollment. Patients who fail screening may be re-screened up to 2 additional times. Patients who are re-screened will undergo all screening procedures and will be assigned a new patient number. Patients will also repeat the informed consent procedure each time they are re-screened.

7.2. Criteria for the Open-Label Extension

7.2.1. Inclusion Criteria for the Open-Label Extension

Based on assessments at the Week 108 visit, a patient will meet all of the following criteria to be eligible for the open-label extension.

1. The patient completed participation in the double-blind period, including the Week 112 visit.
2. The patient or parent/legal guardian (as appropriate) is willing and able to provide signed informed consent for participation in the open-label extension.
3. The patient received blinded study medication throughout the duration of the double-blind period (ie, did not permanently discontinue study medication; see [Section 6.4.2](#)).

7.2.2. Exclusion Criteria for the Open-Label Extension

Based on assessments at the Week 108 and Week 112 visits, a patient who meets any of the following criteria will be excluded from the open-label extension.

1. The patient has progressed to ESRD requiring RRT.
2. The patient developed criteria for discontinuation as defined in [Section 6.4.2](#) or [Section 6.5](#) between Week 108 and Week 112.
3. The patient was unable to initiate, or developed contraindications to, treatment with RAAS inhibitors between Week 108 and Week 112.

4. The patient has an eGFR ≤ 20 mL/min/1.73 m² at Week 108. NOTE: If, in the Investigator's opinion, the eGFR value at Week 108 is deemed unlikely to be representative of the patient's true status, the Investigator may repeat the eGFR measurement prior to Week 112 through the central laboratory to assess patient eligibility. Patients with an eGFR < 30 mL/min/1.73 m² will require close monitoring of eGFR and serum potassium throughout the open-label extension.
5. The female patient is pregnant, plans to become pregnant during the course of the study, or is breastfeeding.

8. TREATMENTS

8.1. Treatments Administered

For the purposes of this protocol, sparsentan is the investigational product, and irbesartan is the active control. When referring to either investigational product (sparsentan) or active control (irbesartan), the term “study medication” is used.

The investigational product doses to be administered in the double-blind period of the study will be dispensed as 200 mg sparsentan tablets over-encapsulated (blinded) with size 00 capsules. The active control doses to be administered in the double-blind period of the study will be dispensed as 75 mg irbesartan tablets over-encapsulated (blinded) with size 00 capsules. The open-label sparsentan doses to be administered in the open-label extension will be dispensed as 200 mg or 400 mg sparsentan tablets.

A dose adjustment will be made for patients whose body weight is ≤ 50 kg at screening; these patients will receive one-half the otherwise specified doses of either sparsentan or irbesartan (weight will be measured at each visit and the dose increased at the Investigator’s discretion if the patient’s weight reaches >50 kg).

8.1.1. Treatments Administered During the Double-Blind Period

Allowed doses during the double-blind period, and the number of capsules to be used for those doses, are shown in Table 2. The full daily dose of study medication will preferably be taken prior to the morning meal, with the exception of the day of a study visit. On the day of a study visit, the patient will take their study medication at the clinic. At the visits specified in [Section 15.1](#), study medication will be administered at the clinic after the pre-dose PK blood sample has been obtained.

Table 2: Sparsentan and Active Control Irbesartan Doses Allowed During the Double-Blind Period

Screening Weight	Initial (or Reduced) Dose		Target Dose		One-Half Initial (or Double Reduced) Dose	
	Number of Capsules ^a	Dose (mg)	Number of Capsules ^a	Dose (mg)	Number of Capsules ^a	Dose (mg)
Randomized to Sparsentan						
>50 kg	2	400	4	800	1	200
20 to ≤ 50 kg	1	200	2	400	N/A	N/A
Randomized to Irbesartan						
>50 kg	2	150	4	300	1	75
20 to ≤ 50 kg	1	75	2	150	N/A	N/A

^a Within each weight category, the number of capsules for each dose category (ie, initial [reduced], target, or one-half initial [double reduced]) are the same for patients randomized to sparsentan and irbesartan, to maintain study blind.

Patients will receive the initial dose (ie, one-half the target dose) based on screening body weight for the first 2 weeks. The Investigator will evaluate dose tolerance in a blinded manner prior to

titrating up to the target dose; tolerance is defined as blood pressure measurements >100/60 mmHg (patients ≥18 years of age) or above the 5th percentile for sex and height (patients <18 years of age; [Banker 2016](#)) after 2 weeks and no adverse events (AEs) or laboratory findings interfering with the patient’s continuation on study medication. Patients who display asymptomatic blood pressure values ≤100/60 mmHg (patients ≥18 years of age) or ≤90/50 mmHg or below the 5th percentile for sex and height (whichever is lower in patients <18 years of age), or who present with clinical symptoms of orthostatic hypotension but otherwise tolerate the initial dose will continue after the Week 2 visit without titrating up to the target dose. At the Investigator’s discretion and in consultation with the Medical Monitor, patients weighing >50 kg who do not tolerate the initial dose for any reason (including changes in laboratory parameters assessed at Week 2) may continue at one-half the initial dose. Patients weighing ≤50 kg who do not tolerate the initial dose for any reason (including changes in laboratory parameters assessed at Week 2) will be discontinued from the study.

The Week 2 PK sample will be drawn prior to escalating the patient to the target dose.

Dose modification is permitted as presented in [Section 8.3.2](#).

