
DOSE/ROUTE/REGIMEN (TEST ARTICLE AND REFERENCE TREATMENT):
 
A dose adjustment will be made for patients whose body weight is ≤ 50 kg at screening; these patients will receive one-half the otherwise specified doses of study medication (weight will be measured at each visit and the dose increased at the Investigator’s discretion if the patient’s weight reaches > 50 kg).
 
Double-blind Period
 
The full daily dose for both sparsentan (active) and irbesartan (control) will preferably be taken prior to the morning meal, with the exception of the day of a study visit. On the day of a study visit, the patient will take their study medication at the clinic. At the visits specified in Section 15.1, study medication will be administered at the clinic after the pre-dose pharmacokinetic (PK) blood sample has been obtained. Allowed doses during the double-blind period are shown in Table 2.
 
Patients will receive the initial dose (ie, one-half the target dose) based on screening body weight for the first 2 weeks. The Investigator will evaluate dose tolerance in a blinded manner prior to titrating up to the target dose; tolerance is defined as blood pressure measurements $> 100/60$ mmHg (patients ≥ 18 years of age) or above the 5th percentile for sex and height (patients < 18 years of age; Banker 2016) after 2 weeks and no adverse events (AEs) or laboratory findings interfering with the patient’s continuation on study medication. Patients who display asymptomatic blood pressure values $\leq 100/60$ mmHg (patients ≥ 18 years of age) or $\leq 90/50$ mmHg or are below the 5th percentile for sex and height (whichever is lower in patients < 18 years of age) or who present with clinical symptoms of orthostatic hypotension but otherwise tolerate the initial dose will continue after the Week 2 visit without titrating up to the target dose (see Section 8.1 and Section 8.3.2).
 
At the Investigator’s discretion, patients weighing > 50 kg who do not tolerate the initial dose for any reason (including changes in laboratory parameters assessed at Week 2) may continue at one-half the initial dose. Patients weighing ≤ 50 kg who do not tolerate the initial dose for any reason (including changes in laboratory parameters assessed at Week 2) will be discontinued from the study.
 
Open-label Extension
 
The full daily dose will preferably be taken prior to the morning meal. Allowed doses during the open-label extension are shown in Table 3.
 
Patients who are taking 2 capsules of study medication (ie, 400 mg sparsentan or 150 mg irbesartan) at the end of the double-blind period will initiate treatment in the open-label extension at 200 mg sparsentan for the first 2 weeks of the open-label extension. Likewise, patients who are taking 4 capsules of study medication (ie, 800 mg sparsentan or 300 mg irbesartan) at the end of the double-blind period will initiate treatment in the open-label extension at 400 mg sparsentan for the first 2 weeks of the open-label extension. Following 2 weeks
	

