

NAME OF COMPANY: Travere Therapeutics, Inc.
	
NAME OF FINISHED PRODUCT: sparsentan tablets

(ie, Week 114) at one-half the double-blind dose, the Investigator will evaluate dose tolerance, as defined above for the double-blind period, prior to titrating up to the target dose. If the patient is tolerating the initial dose, the patient will titrate to the target dose at this time. Patients who display asymptomatic blood pressure values $\leq 100/60$ mmHg (patients ≥ 18 years of age) or $\leq 90/50$ mmHg or are below the 5th percentile for sex and height (whichever is lower in patients < 18 years of age) or who present with clinical symptoms of orthostatic hypotension but otherwise tolerate the initial dose will continue without titrating up to the target dose after the Week 114 visit.
 
Patients who are taking 1 capsule of study medication (ie, 200 mg sparsentan or 75 mg irbesartan) at the end of the double-blind period will initiate treatment in the open-label extension at 200 mg sparsentan for the first 2 weeks of the open-label extension. Following 2 weeks at 200 mg sparsentan (ie, Week 114), the Investigator will evaluate dose tolerance, as defined above for the double-blind period. Patients who are tolerating the initial dose will continue on 200 mg sparsentan at this time, including those who display asymptomatic blood pressure values $\leq 100/60$ mmHg (patients ≥ 18 years of age) or $\leq 90/50$ mmHg or are below the 5th percentile for sex and height (whichever is lower in patients < 18 years of age) or who present with clinical symptoms of orthostatic hypotension but otherwise tolerate the initial dose.
 
For patients who enter the open-label extension with an eGFR value < 30 mL/min/1.73 m² (ie, at Week 108), any dose titration at Week 114 will be at the Investigator’s discretion based on the results of the Week 114 assessments. Patients who do titrate to a higher dose at Week 114 will be contacted by the Investigator at Week 116 to assess tolerance of the higher dose; at the Investigator’s discretion, these patients may also come in for an additional visit at this time.
 
Doses may be modified at any time throughout the open-label extension for safety/tolerability reasons at the Investigator’s discretion. In addition, after titration to the target dose, increases above the target doses of 200 or 400 mg sparsentan may be considered for patients who, in the Investigator’s opinion (and following consultation with the Medical Monitor), would benefit from an increased dose.
	

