Patients who are taking 1 capsule of study medication (ie, 200 mg sparsentan or 75 mg irbesartan) at the end of the double-blind period will initiate treatment in the open-label extension at 200 mg sparsentan for the first 2 weeks of the open-label extension. Following 2 weeks at 200 mg sparsentan (ie, Week 114), the Investigator will evaluate dose tolerance (as defined in [Section 8.1.1](#)). Patients who are tolerating the initial dose will continue on 200 mg sparsentan at this time, including those who display asymptomatic blood pressure values $\leq 100/60$ mmHg (patients ≥ 18 years of age) or $\leq 90/50$ mmHg or are below the 5th percentile for sex and height (whichever is lower in patients < 18 years of age) or who present with clinical symptoms of orthostatic hypotension but otherwise tolerate the initial dose.

For patients who enter the open-label extension with an eGFR value < 30 mL/min/1.73 m² (ie, at Week 108), any dose titration at Week 114 will be at the Investigator's discretion based on the results of the Week 114 assessments. Patients who do titrate to a higher dose at Week 114 will be contacted by the Investigator at Week 116 to assess tolerance of the higher dose; at the Investigator's discretion, these patients may also come in for an additional visit at this time.

Dose modification is permitted during the open-label extension as presented in [Section 8.3.2](#).

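### For patients under 18 in the double-blind period, the Week 2 tolerance limit and the asymptomatic hold limit do not match, so some low readings fall between two dosing rules

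*Protocol*

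**What the plan says.** Section 8.1.1 sets three rules for the Week 2 visit. P5 below means the 5th percentile for sex and height.

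- **Tolerance.** "The Investigator will evaluate dose tolerance in a blinded manner prior to" titration. Adults pass at >100/60 mmHg; patients under 18 pass if their pressure is "or above the 5th percentile for sex and height".
- **Hold.** Asymptomatic adults at ≤100/60 mmHg, and asymptomatic patients under 18 at "≤90/50 mmHg or below the 5th percentile for sex and height (whichever is lower in patients <18 years of age"), who "otherwise tolerate the initial dose will continue after the Week 2 visit without titrating up to the target dose".
- **Non-tolerance.** "Patients weighing ≤50 kg who do not tolerate the initial dose for any reason" are discontinued from the study. Those above 50 kg may go to half the initial dose, at the Investigator's discretion and in consultation with the Medical Monitor. Table 2 offers the lighter group no lower dose.

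The synopsis (Dose/Route/Regimen) has the same tolerance limit, and its hold limit again applies to children who "are below the 5th percentile for sex and height (whichever is lower in patients < 18 years of age"). Section 8.3.2 repeats the hold limit and the ≤50 kg rule. For the open-label extension, the synopsis holds patients with the same low readings who "otherwise tolerate the initial dose will continue without titrating up to the target dose after the Week 114 visit", and 8.1.2 matches it. SAP 4.2.1 refers back to the protocol for the tolerability rules.

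**The concern.** The tolerance and hold limits should divide asymptomatic readings between them. The adult pair does so on each component. The paediatric pair does not: the tolerance limit is always P5, while the hold limit is the lower of P5 and 90/50. The words about whichever is lower themselves allow that 90/50 is sometimes the lower one.

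A child whose reading falls between the two limits has not met the definition of tolerance and is not named in the hold sentence. The only other double-blind rule is the one for non-tolerance, which is mandatory at ≤50 kg. At stake are an unintended discontinuation, or, if a site applies only the hold sentence, an unintended dose increase in a child at or below P5.

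**Working it through.** There is no plan figure to reproduce. The check lists the whole-mmHg readings that meet neither rule, taking systolic and diastolic separately.

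**Inputs.** The tolerance and hold limits are from 8.1.1. Let L be the fixed limit: 90 systolic, 50 diastolic. P5 values are not in the documents (a chart is cited), so those below are assumptions.

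**Rules for patients under 18**
- Tolerated: BP > P5.
- Held: BP ≤ L if P5 > L; BP < P5 if P5 < L.
- Uncovered: neither.

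**Result**
- P5 > L: uncovered readings satisfy L < BP ≤ P5, which is P5 − L whole-mmHg values.
- P5 < L: only BP = P5, one value.
- P5 = L: none if the two limits are treated as equal, so that ≤L applies; one (the value L) if strictly below L is taken as the lower limit.

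| Component | Assumed P5 | Uncovered readings | Count |
|---|---|---|---|
| Systolic (L = 90) | 88 | 88 | 1 |
| | 92 | 91–92 | 92 − 90 = 2 |
| | 96 | 91–96 | 96 − 90 = 6 |
| | 100 | 91–100 | 100 − 90 = 10 |
| Diastolic (L = 50) | 48 | 48 | 1 |
| | 52 | 51–52 | 52 − 50 = 2 |
| | 56 | 51–56 | 56 − 50 = 6 |
| | 60 | 51–60 | 60 − 50 = 10 |

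**Literal consequence.** Take two asymptomatic children of ≤50 kg with systolic P5 = 95 (assumed) and diastolic pressure above its limits. At systolic 93 the child fails tolerance (93 is not above 95) and is not held (93 is above 90), so the mandatory rule applies. At systolic 88 the child also fails tolerance but is held (88 ≤ 90). The milder reading has the harsher outcome.

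**Adult comparison.** >100 against ≤100, and >60 against ≤60, leave nothing uncovered on either component. This holds only component by component. If each limit requires both numbers, an adult at 110/58 meets neither: 58 is not above 60, and 110 is not ≤100.

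**Check of the fix.** Let tolerance mean both components above P5, and hold mean either component at or below P5. The second statement is the negation of the first, so no reading is uncovered at any P5. The same convention closes the adult case: 110/58 is held because 58 ≤ 60.

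**The case against.** The strongest reply is that the protocol already points to holding. Tolerance is assessed before titration, so a child not above P5 does not pass to the target dose. The hold sentence concerns patients who otherwise tolerate the initial dose, which implies that a low reading alone is not intolerance. Section 8.1.2, using the same definition for patients on one capsule, says so more directly: "Patients who are tolerating the initial dose will continue on 200 mg sparsentan at this time, including those who display asymptomatic blood pressure values" at or below the limits. Holding is reversible, because 8.3.2 allows later titration. This stands as evidence of intent, but no double-blind text says it for the uncovered readings, and the SAP adds no rule of its own.

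A second reply is that the two hold conditions could be read as a plain *or*. Then a reading is uncovered only when it equals P5 and P5 exceeds 90/50 (92, 96 or 100 in the systolic examples). That reading ignores the words about whichever is lower.

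Third, the width of the gap depends on a chart that the documents do not reproduce, and the adult contrast depends on reading each component separately. Both are right and limit the claim.

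Fourth, replacing the 90/50 limit raises the hold threshold wherever P5 exceeds 90/50. That is a dosing-rule change, and 13.3 requires protocol changes to be documented in an amendment.

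A reader might go further and infer that the protocol intends to remove these children, that many would be lost, or that the eGFR slope comparison is compromised. The documents do not support this: the intent to hold is evident, no count of affected children can be derived, and nothing in the statistical plan depends on these limits.

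**Conclusion.** The mismatch is real and minor. It is a conflict between stated dosing rules in the double-blind period: followed to the letter, it discontinues a child of ≤50 kg for a milder asymptomatic reading than one that is merely held. It spans several mmHg only if P5 exceeds 90/50 on a component; below that it is a single reading.

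The conclusion rests on reading the limits component by component and taking the lower-of-two wording as written; the band widths rest on assumed P5 values. The number of children with such a reading at Week 2 cannot be computed, but is likely small: patients under 18 enrol only at US and UK sites. No endpoint, analysis, sample size or power figure changes.

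The literal discontinuation outcome should not be carried over to the open-label extension. Footnote a to Table 3 lets patients who do not tolerate the initial dose stay on it at the Investigator's discretion, so matching the hold wording there is for consistency.

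**What to change.** By protocol amendment, in the double-blind text of the synopsis, 8.1.1 and 8.3.2, replace the paediatric part of the hold sentence with wording such as:

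*A symptom-free patient under 18 whose systolic or diastolic pressure is at or below the 5th percentile for sex and height, and who has no other intolerance of the initial dose, stays on that dose and is not titrated. Such a reading alone is not non-tolerance and does not trigger the ≤50 kg discontinuation rule.*

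Use matching hold wording in 8.1.2 and the open-label part of the synopsis. State that failing the limit on either component counts, for adults as well. Leave unchanged the Investigator's discretion to reduce or stop the dose for safety (6.4.2, 8.3.2, 9.6).

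The cost is the amendment itself, with no new data or visits. Slightly fewer children would titrate at Week 2 than under the present hold sentence alone, with later titration still open under 8.3.2.
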